9.9. Trial Process Evaluation

Quantitative data collection in relation to nurses and treatment sessions: We will collect data about the number of nurses trained and the number of participants treated per nurse; number of SRT appointments attended per participant (face-to-face and/or telephone) and duration of appointments (mins); prescribed sleep window times for each intervention week for each participant; completion rate of sleep diaries during intervention; and intervention adherence (number of nights per week participant adheres [within 15 mins] to prescribed bed and rise-time).

9.10. Early Discontinuation/Withdrawal of Participants

Each participant has the right to withdraw from the trial at any time, without the need to provide a reason and in knowledge of the fact that withdrawing from the trial will not affect their future care from their healthcare provider. However, de-identified data that have already been collected and incorporated in the study database will be included in the analysis (and any personally identifiable data will be destroyed). In addition, the Investigator may discontinue a participant from the trial (or intervention) at any time if the Investigator considers it necessary for any reason including, but not limited to:

- Ineligibility (either arising during the trial or retrospectively)
- For safety reasons, rendering participation in the trial or intervention inappropriate

In the event of an investigator withdrawal, the reason will be recorded on the eCRF.

A participant may wish to discontinue their treatment and/or withdraw from follow-up data collection. If a participant wishes to discontinue their treatment, the study team will contact the participant and ask if they are still willing to participate in the collection of follow-up data. Participants that continue to participate in follow-up data collection will not be considered a withdrawal. If a participant wishes to withdraw from follow-up data collection, data collected up to the point of withdrawal will still be used, as detailed in the PIS.

The reason for withdrawal, if provided, will be recorded on the eCRF.

No participants will be replaced if they are discontinued or withdraw.

9.11. Internal Pilot Phase and Stop-Go Criteria

We will incorporate a four-month internal pilot phase to test trial procedures and determine trial progression against measurable "stop-go" criteria in consultation with the Trial Steering Committee (TSC) and NIHR. Trial progress in relation to recruitment and retention will be monitored monthly by the Trial Management Group (TMG). If progress is below target, remedial strategies will be implemented (e.g., recruitment of additional practices and trained nurses).

Pre-specified stop/go criteria (see Tables 9 and 10 below) will be assessed by the Trial Steering Committee (TSC) in relation to recruitment (at the end of month 4) and treatment session fidelity (at the end of month 8). We aim to recruit 63 participants within four months of the first participant being randomised.

Recruitment Criteria (% of target n=63 at month 4)	Number of participants recruited	Proposed Action
100%	63	Progress to main trial phase
50-99%	32-62	Discuss progress with TSC and NIHR:EME and implement strategies (e.g., recruitment of additional practices and/or nurses)
<50%	<32	Consider stopping trial, discuss with TSC and NIHR:EME

Table 9: "Stop-Go" Recruitment Criteria

Table 10: "Stop-Go" Treatment Fidelity Criteria

Treatment Fidelity Criteria (available complete session recordings assessed at month 8)	Proposed Action
≥70% of SRT elements are covered	Progress to main trial phase
60-69% of SRT elements are covered	Discuss with TSC and NIHR:EME, implement strategies (e.g., nurse re-training, additional nurses)
<60% of SRT elements are covered	Consider stopping trial, discuss with TSC and NIHR:EME

Clinical Research Protocol Template version 15.0

© Copyright: The University of Oxford and Oxford University Hospitals NHS Foundation Trust 2019 Page 31 of 52

9.12. Definition of End of Study

The end of the study will be the last data capture of last participant.

10. SAFETY REPORTING

10.1. Serious Adverse Event Definition

A serious adverse event (SAE) is any untoward medical occurrence that:

- results in death
- is life-threatening
- requires inpatient hospitalisation or prolongation of existing hospitalisation
- results in persistent or significant disability/incapacity
- Consists of a congenital anomaly or birth defect.

All participants, and the research nurses facilitating SRT, will be prompted to self-report SAEs. Along with self-reporting of SAEs, we will also ask participants about unplanned hospitalisations (as opposed to elective procedures or planned admissions for treatment) as part of the assessments at 4, 8, and 26 weeks, and follow-up participants who report being hospitalised.

We will record planned hospital admissions at baseline and when they occur, these will not be counted as SAEs. SAEs will be assessed for severity, seriousness, and relatedness to study procedures by a medically qualified member of the team. SAEs will be reported and followed up from date of randomisation until either the date of trial withdrawal or 26-week follow-up completion, whichever is earlier. Any SAEs that are continuing at trial withdrawal or 26-week follow-up completion will be marked as "Continuing" at the end of the study.

Other adverse events that require medical intervention may also be considered a serious adverse event when, based upon appropriate medical judgement, the event may jeopardise the participant and may require medical or surgical intervention to prevent one of the outcomes listed above.

NOTE: The term "life-threatening" in the definition of "serious" refers to an event in which the participant was at risk of death at the time of the event; it does not refer to an event which hypothetically might have caused death if it were more severe.

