9.4. Randomisation

Following baseline assessments, participants will be eligible for randomisation. Eligible participants will be randomised to SRT+TAU (135 participants) or TAU (115 participants) using a secure, validated and compliant web-based randomisation system (Sortiton), with a non-deterministic minimisation algorithm to ensure practice, use of antidepressant medication (yes/no), current receipt of psychological therapy for depression (yes/no), age (18-65yrs vs. >65yrs), sex (male/female/other), baseline insomnia severity (ISI score: <22 vs. 22-28) and depression severity (PHQ-9 score: <19 vs. 19-27) are balanced across the two groups. Individual randomisation is appropriate because the risk of control group contamination is very low: treatment will be delivered by trained research nurses who will be independent from the practice and will only interact with participants in the experimental arm.

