- ECAT: the ECAT assesses speed to respond to positive and negative self-referent personality descriptors. Participants are asked whether they would 'like' or 'dislike' to be referred to as each characteristic. The task takes approximately 5 minutes to complete. Mean reaction time for correct responses for positive and negative words will be considered as the main outcomes for this task. THE ECAT also serves as the stimulus set for the subsequent free recall (see EREC below).
- EREC: Participants are asked to write down (type) as many of the words previously presented in the emotional categorisation task (ECAT), in a 2-minute interval. The recall of emotional words gives a measure of bias for both positive and negative words. The main outcome measures are number of positive and negative self-referent words correctly recalled.

Participants will be provided with an actigraph watch (a device which measures movement to infer sleep/wake periods and environmental light exposure) and instructions on its use. The researcher will review instructions with the participant to ensure they are clear on its use and ask them to wear the watch for the next seven days. Concurrently, participants will record a modified daily sleep diary (CSD; 25) for seven days to capture nightly subjective sleep and daytime activation. On completion, participants will return the diary and watch through either 1) recorded-delivery postage; 2) direct delivery to the researcher's office or local practice; or 3) arrange for the researcher to collect directly from the participant.

On return of sleep diary and actigraph watch, participants will be randomised by a member of the research team to either SRT+TAU or standalone TAU. The SRT+TAU group will meet with the trained nurse on six occasions over approximately an eight-week period to receive guidance on the rationale and implementation of SRT (see *Interventions* below).

Questionnaires will be collected electronically unless the server is unavailable or a participant requests to complete the questionnaire in paper form. Tasks will be completed on a study laptop if held in person, or completed online using the participant's device (e.g., laptop, desktop, or tablet) if the visit is completed remotely.

Table 7: Data c	collection at	baseline visit
-----------------	---------------	----------------

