11.2. Description of the Statistical Methods

In accordance with CONSORT guidelines, we will record and report participant flow. Descriptive statistics of recruitment, drop-out, and completeness of interventions will be provided. The primary analysis will be according to randomised treatment assignment and will include all randomised participants for whom data are available, as defined by protocol eligibility. Baseline variables will be presented by randomised group using frequencies (with percentages) for binary and categorical variables and means (and standard deviations) or medians (with lower and upper quartiles) for continuous variables. There will be no tests of statistical significance nor confidence intervals for differences between groups on any baseline variables. The results from the trial will be presented as comparative summary statistics (difference in proportions or means) with 95% confidence intervals. All tests will be done at a 5% two-sided significance level. The study results will be reported in accordance with the CONSORT 2010 statements and a full detailed statistical analysis plan will be prepared before recruitment starts.

The primary comparison is the mean difference in the primary outcome (PHQ-9 score) at 26 weeks for all randomised participants, as defined by protocol eligibility criteria, regardless of what intervention they actually received or compliance of intervention. A multi-level model will be fitted to the data with PHQ-9 score at 4-, 8- and 26-weeks post-randomisation, adjusting for minimisation factors and baseline score. Practice and participant will be included as random effect and an interaction term for the treatment by time interaction will allow the treatment effect to differ at each time point. "Therapist effect" (i.e. effect from the intervention being delivered by the same nurse) will also be considered in the model. A similar approach will be used for secondary (mechanistic) outcomes. Numbers of participants who experienced serious adverse events will be compared in the safety population using Chi-square or Fisher's exact test. Pre-specified subgroup analyses of the primary outcome will be explored by baseline depression severity, insomnia severity, and antidepressant medication use at baseline.

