11.4. Analysis populations

The primary analysis population will be all randomised participants, as defined by protocol eligibility criteria, regardless of what intervention they actually received, compliance of intervention, or completion of outcome. We will also perform exploratory Compiler Average Causal Effect (CACE) analysis to assess the effects of minimum treatment compliance (defined as attending at least 3 treatment sessions) and full treatment compliance (attending all 6 treatment sessions) on the primary outcome.

The safety population will consist of participants who engaged to some extent (defined as attending at least one session of SRT), according to the treatment they actually received (as-treated).

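### SRT nurses are an extra SAE reporting channel in one arm only, so the planned between-arm SAE test may lean slightly against SRT

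*Protocol*

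**What the plan says.** - **Who reports.** Protocol section 10.1: "All participants, and the research nurses facilitating SRT, will be prompted to self-report SAEs". No matching staff reporter is named for TAU.
- **What both arms share.** All participants are prompted to report SAEs. In addition, section 10.1 says that "we will also ask participants about unplanned hospitalisations" at the 4-, 8- and 26-week assessments.
- **Whom the nurses see.** Section 9.4 says the treating nurses "will only interact with participants in the experimental arm".
- **For how long.** Section 9.7 has SRT participants "meet with the trained nurse on six occasions over approximately an eight-week period". The schedule in Appendix B (Table 11) puts the six sessions in a six-week period.
- **Reporting period.** Section 10.1: "SAEs will be reported and followed up from date of randomisation until either the date of trial withdrawal or 26-week follow-up completion".
- **The comparison.** Section 11.2: "Numbers of participants who experienced serious adverse events will be compared in the safety population", by chi-square or Fisher's exact test. Nothing in the protocol limits this to events from channels open to both arms, or asks for the source of each event to be recorded.

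**The concern.** A between-arm comparison of SAE counts is fair only if an event has the same chance of being recorded in either arm. Here an SRT participant who does not mention an event to the research team may still mention it at one of six nurse sessions. A TAU participant has no such second route. Unless self-report is complete, or nurses add nothing to it, the recorded risk in SRT exceeds that in TAU even when the true risks are equal.

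Two features add to this. Section 10.1 lets other events needing medical intervention be classed as SAEs on medical judgement, and such events count only if somebody hears of them. Section 11.3 allows up to 20% attrition. A TAU participant who misses an early assessment loses that hospitalisation question, whereas an SRT participant in the same position may still be in touch with a nurse.

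At stake is the reading of the SAE comparison: an apparent small excess under SRT could come partly from contact alone. Case-level safety oversight is not at stake, and nurse reporting helps it.

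**Working it through.** The protocol states no SAE rate, no capture rate and no figure for the SAE test, so there is no plan figure to reproduce. What follows is an illustration.

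**Inputs from the protocol**
- Arms: 135 SRT and 115 TAU (section 11.3). All are assumed to be in the comparison.
- SAE reporting period: 26 weeks (section 10.1).
- Nurse contact: about 8 weeks (section 9.7) or 6 weeks (Table 11).
- Test level: 5% two-sided (section 11.7).

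**Assumptions not in the protocol**
- True SAE risk *p* is the same in both arms (5% to 10% shown).
- A share *s* of events is captured through participant channels, the same in both arms (50% to 90%).
- Events, and missed events, are spread evenly over 26 weeks.
- Nurses catch every otherwise missed event while they are in contact. This is the most unfavourable case for the given contact period.

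**Formulae**
- Share of follow-up with nurse contact: *f* = 8/26 = 0.308, or 6/26 = 0.231.
- Recorded risk in TAU = *p* × *s*.
- Recorded risk in SRT = *p* × [*s* + (1 − *s*) × *f*].
- Spurious risk ratio = 1 + *f* × (1 − *s*)/*s*, which does not depend on *p*.
- Extra SRT participants with a recorded SAE = 135 × *p* × (1 − *s*) × *f*.

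**Spurious risk ratio**

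| Self-report capture *s* | 8 of 26 weeks | 6 of 26 weeks |
|---|---|---|
| 90% | 1.03 | 1.03 |
| 85% | 1.05 | 1.04 |
| 70% | 1.13 | 1.10 |
| 60% | 1.21 | 1.15 |
| 50% | 1.31 | 1.23 |

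Example at *s* = 70%, 8 weeks: 1 + 0.308 × 0.30/0.70 = 1.13.

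**Counts and test behaviour, 8 of 26 weeks, no true difference.** The last column is the exact probability that Fisher's test rejects with SRT higher. The first value has both arms at the TAU recorded risk; the second has the extra nurse channel.

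| *p* | *s* | Recorded SRT vs TAU | Extra SRT participants | Fisher rejection against SRT |
|---|---|---|---|---|
| 5% | 90% | 4.65% vs 4.50% | 0.2 | 1.8% to 2.1% |
| 5% | 70% | 3.96% vs 3.50% | 0.6 | 1.6% to 2.6% |
| 10% | 50% | 6.54% vs 5.00% | 2.1 | 1.8% to 5.6% |

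Example, second row: 135 × 0.05 × 0.30 × 0.308 = 0.6.

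If nurses catch only half of the otherwise missed events in 8 weeks, the excess in the risk ratio halves, for example to 1.07 at 70% capture.

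**The case against.** The strongest case on the other side has four parts.

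**The effect is small.** Both arms get the general prompt to report SAEs as well as the hospitalisation questions at weeks 4, 8 and 26. Nurse contact falls mainly in the first eight weeks, when both arms are asked twice and recall is shortest. This stands, and it sets the size of the point.

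A reader might infer a much larger bias by supposing that nurse contact lifts SRT capture to 90% over the whole follow-up. Against 70% or 60% in TAU, that would give 0.90/0.70 = 1.29 or 0.90/0.60 = 1.5. The schedule does not support it. Nurses would have to recover (0.90 − 0.70)/(1 − 0.70) = 67% or (0.90 − 0.60)/(1 − 0.60) = 75% of missed events while present for at most 8/26 = 31% of the period. Missed events would have to cluster early, and nothing in the protocol suggests that they do.

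**Restricting the test would do harm.** A reader might conclude that the main comparison should use only events elicited by the week-4, 8 and 26 questions. Section 10.1 specifies those as questions about unplanned hospitalisation. A death cannot be elicited that way, and life-threatening or disabling events without admission could be lost, as could events in participants who miss an assessment. This objection stands, so the all-source table must be kept.

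**Details belong elsewhere.** The SAE form, the SAP and the DMC charter are not shown and may already record source. Section 11.2 also does not say in terms that events from every source are counted; that is the natural reading, because nothing limits it. This is fair, and it is a reason for low severity. The unequal channel and the test are nevertheless both fixed in the protocol, and source cannot reliably be recovered later if it is not captured at reporting.

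**Interpretation does not rest on a raw count.** A medically qualified team member assesses seriousness and relatedness (section 10.1), and extra contact is inherent in comparing a delivered therapy with usual care. This is true, but the planned test is still on the number of participants with an SAE.

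Separately, section 11.4 defines the safety population by attendance at an SRT session or more and leaves TAU membership unclear. That needs reconciling with section 11.2 but is a different point.

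**Conclusion.** The point holds as a minor one. The protocol gives SRT an SAE reporting channel that TAU does not have, during about the first 6 to 8 of 26 weeks, and then tests SAE counts between arms. If participant self-report is incomplete and nurses learn of some missed events, the comparison is biased, and the direction is against SRT.

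The size cannot be derived from the protocol. With even timing of events and full nurse capture over 8 of 26 weeks, the spurious risk ratio is about 1.03 to 1.21 for self-report capture of 90% down to 60%, and about 1.3 only at 50%. This amounts to about 0.2 extra SRT participants (5% risk, 90% capture) to about 2 (10% risk, 50% capture). It would be larger if missed events clustered during nurse contact, and smaller if nurses caught fewer of them.

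The documents do not support saying that the comparison is uninterpretable or that a false finding of harm is likely.

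**What to change.** 1. Record the source of each SAE: participant report or assessment, nurse, or other.
2. Ask the same SAE and hospitalisation questions in both arms at weeks 4, 8 and 26, whether or not a nurse has already reported the event. Otherwise an event told to a nurse may not be repeated, and would wrongly look nurse-only.
3. Keep the all-source SAE table, including all deaths.
4. Prespecify a companion between-arm comparison that leaves out events known only through an SRT nurse, but keeps every death and every event reported through a channel open to both arms.
5. List nurse-only events separately.

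Nurse reporting for safety oversight is unchanged.

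**Cost:** one field on the SAE form, one extra analysis with a sentence to define it, and slightly fewer events in the companion comparison.

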10.3. Other Adverse Events

We will record incidences of falls, accidents (road-traffic accidents and work-related injuries), near miss driving incidents, and falling asleep while driving alongside outcomes at baseline, 4-, 8-, and 26-weeks post-randomisation. We will also assess proportion of each group showing an increase in suicidal ideation using item 9 from the PHQ9. As above, these outcomes will be assessed at baseline, 4-, 8-, and 26-weeks post-randomisation.

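### The exemption of planned admissions from SAEs has no limit on timing or cause, and the direct follow-up question omits planned admissions, so some admissions arranged after randomisation for new or worsening illness can be missed

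*Protocol*

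**What the plan says.** Four statements in Protocol section 10.1 bear on this.

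- **Definition.** An untoward medical occurrence is serious if, among other criteria, it "requires inpatient hospitalisation or prolongation of existing hospitalisation". The criterion does not separate scheduled from emergency admissions.
- **Window.** "SAEs will be reported and followed up from date of randomisation", ending at withdrawal or completion of the 26-week follow-up, whichever is earlier.
- **Exemption.** "We will record planned hospital admissions at baseline and when they occur, these will not be counted as SAEs".
- **Direct question.** At weeks 4, 8 and 26, "we will also ask participants about unplanned hospitalisations (as opposed to elective procedures or planned admissions for treatment").

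The same section gives two more general routes. One is a prompt: "All participants, and the research nurses facilitating SRT, will be prompted to self-report SAEs". The other is discretionary: "Other adverse events that require medical intervention may also be considered a serious adverse event when, based upon appropriate medical judgement", where the event may put the participant at risk and may need treatment to prevent one of the listed outcomes. Section 10.3 adds items on specific harms: "We will record incidences of falls, accidents (road-traffic accidents and work-related injuries), near miss driving incidents, and falling asleep while driving", together with increases in suicidal ideation on PHQ-9 item 9.

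**The concern.** An exemption for planned admissions exists to keep routine care for stable, long-standing conditions out of the SAE count. For that purpose it should depend on whether the condition was there before randomisation and has stayed unchanged. As worded, it depends only on whether the admission was planned, and it does not say planned by when.

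The admissions that matter most for safety in a depressed, sleep-restricted population need not be emergencies. A participant may fall in week 3 and be booked for surgery in week 5. Another may deteriorate in week 10 and have an admission arranged for week 12. In both, the untoward event and the booking fall after randomisation.

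Three uses depend on SAE status: the assessment of severity and relatedness (section 10.1), the report to the ethics committee of related and unexpected events (section 10.2), and the comparison between groups of the number of participants with SAEs (section 11.2). An admission classed as exempt drops out of all three.

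**Working it through.** The protocol states no figure to reproduce, and no arithmetic applies. The check sets the statements of section 10.1 against each other for one case: an admission arranged after randomisation for a new injury or a worsened condition.

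**Step 1. Does the case meet the definition?** Yes. There is an untoward occurrence, it leads to inpatient admission, and it falls inside the SAE window.

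**Step 2. Is it exempt?** The exemption sentence supports two readings.

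- *Broad:* any planned admission is recorded, whether known at baseline or arising later, and none counts as an SAE.
- *Narrow:* only admissions already planned at baseline are meant. They are logged then and again when they take place.

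**Step 3. Does the direct question ask for it?** On either reading, no. The question sets unplanned admissions against elective procedures and planned admissions for treatment, with no reference to when the plan was made.

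| Reading of the exemption | Should it count as an SAE? | Does the direct question ask for it? | Result |
|---|---|---|---|
| Broad | No | No | Meets the definition, then is removed by the exemption |
| Narrow | Yes | No | Should count, but the direct question omits it |

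Choosing between the readings therefore does not remove the problem. It only moves it from classification to ascertainment.

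**Step 4. Do the other routes close the gap?**

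- *Recording planned admissions when they occur.* This may bring the admission to light, but on the broad reading it still does not count. The schedule of events in Appendix B has no separate row for hospital admissions after baseline.
- *Prompted self-report of SAEs.* This is a real route with no stated limit to unplanned admissions. It relies on someone recognising the event as serious, under a section that says planned admissions are not SAEs. The research nurses are one of the two reporting sources, and section 9.4 says they see only participants in the SRT arm, so that part of the route is not the same in both arms.
- *Medical judgement.* The clause is permissive and concerns other adverse events. It does not say that it overrides the exemption.
- *Items in section 10.3.* These would record the fall, the accident or the increase in suicidal ideation. They are listed as other adverse events, and the section provides for neither a relatedness assessment nor ethics committee reporting.

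Some of these routes will catch some of the admissions. None catches them by rule.

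**The case against.** The strongest reply is that the narrow reading is the natural one. Recording planned admissions at baseline has little purpose unless it identifies those already arranged, and section 8.3 uses planned in that forward-looking sense when it excludes people with major surgery planned during treatment. The untoward event is also the fall or the deterioration, not the booking, and a medically qualified team member assesses seriousness. On this view only a clarifying phrase is needed.

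Much of this stands. The narrow reading is open, and the event behind an admission could qualify by another criterion or by judgement. But the protocol does not state the narrow reading, and the follow-up question does not follow it.

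A reader might infer more than the text supports, in three ways.

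- *That every planned admission is excluded.* That is one of two readings.
- *That such admissions are never asked about.* Section 10.1 prompts for SAEs in general and records planned admissions as they occur, and section 10.3 asks about falls, accidents and suicidal ideation. Only the direct hospitalisation question leaves them out.
- *That a given number of events is lost, or that the direction of the SAE comparison could be reversed.* The protocol gives no admission rate and no share of admissions arranged after randomisation. The exemption and the direct question apply to both arms, and no difference between arms in their effect has been shown.

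A further caution concerns the remedy. If the exemption were confined to admissions booked before randomisation, elective care for a stable condition booked during follow-up would count as an SAE although nothing untoward had happened. The wording of the fix has to allow for that.

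**Conclusion.** The point holds as a gap in a stated safety rule. The definition, the exemption and the direct question in section 10.1 do not fit together for admissions arranged after randomisation because of new or worsening illness or injury. On one reading these are not counted. On the other they should count but are not asked for directly. Whether any given case is captured then depends on general self-report or medical judgement.

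The size cannot be estimated from the documents. The conclusion rests on the wording alone and needs no assumption about event rates. It does not touch the primary outcome. It merits correction because the SAE definition and its ascertainment belong to the protocol itself, and because the between-group SAE comparison is only as complete as the events that reach it.

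**What to change.** Make two changes in section 10.1.

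1. **Exemption.** State that an admission is exempt only if it is for a pre-existing condition that has not worsened since randomisation, and it was either planned before randomisation or is elective. This keeps routine care for stable conditions out of the SAE count, including when it is booked during follow-up.
2. **Follow-up item.** At weeks 4, 8 and 26, ask about any hospital admission, its reason and when it was arranged. Have the medically qualified assessor apply the exemption, so that the participant does not have to judge what counts as planned.

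The cost is one sentence, one reworded questionnaire item and a few more admissions to classify. Treatment, visits and the primary analysis do not change.
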